6.4 STUDY INTERVENTION COMPLIANCE

In order to verify compliance with the study procedures, the completion of case report forms is required for each study visit for participants. These records will be periodically reviewed investigator(s) to ensure all study procedures were adequately performed. In addition, investigator(s) will cross reference the documented information against the randomization schema to ensure participants were appropriately randomized and administered the procedures as specified.

7 STUDY DISCONTINUATION AND PARTICIPANT WITHDRAWAL

7.1 DISCONTINUATION OF STUDY INTERVENTION

Discontinuation of taVNS does not necessarily mean discontinuation from the study, as remaining study procedures may be completed as indicated by the study protocol. If a clinically significant finding is identified after enrollment, a qualified investigator will determine if any change in participant management is needed. Also, the participant may be notified of the finding and recommended to seek further clinical evaluation and care.

7.2 PARTICIPANT DISCONTINUATION/WITHDRAWAL FROM THE STUDY

Given that participation in this study is voluntary, participants may elect to withdraw at any time by notifying a researcher. It is also possible that participation in this study may end without the participant's consent. This decision may be made by a researcher, the Northwell Health Human Research Protection Program, or a federal or state regulatory agency.

Reasons for withdrawal may include: failure to comply with study requirements; failure to keep study appointments; a change in their medical history, medications, or lifestyle (including alcohol, tobacco, or substance usage) that results in them no longer meeting study eligibility; inability to tolerate study procedures; it is not in the participant's best interest to continue on this study; or the study is stopped.

Participants that prematurely withdraw from the study due to an adverse event will be followed (e.g. telephone contact, follow-up visits, etc.) until resolution of the event or they indicate they no longer want to be contacted. In addition, a designated investigator will have access to treatment status at all times and provide that information to appropriate medical personnel in the event of medical emergencies. If the participant withdraws from this study or if s/he is withdrawn from the study, any data already collected will continue to be used, but no new data will be collected. The reason for participant discontinuation or withdrawal from the study will be recorded.

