There is a risk that some of the questions involved in the assessments could cause potential stress or discomfort. The investigative team will vigilantly observe each participant's emotional reactions during all study procedures, and offer referrals when appropriate. If the mental health symptoms of any participant were to worsen, [name] would be responsible for assessing and referring for treatment within the WTC Health Program. Given the exclusion criteria (no signs of psychosis, mania, bipolar disorder, active substance dependence, or suicidal/homicidal intent) we hope to limit the likelihood of adverse events regarding mental health symptoms.

Aim 2: taVNS

The taVNS device is Nesos MAUI PROTECT System— a wearable, external stimulator that generates electrical pulses transcutaneously delivered to the auricular branch of the vagus nerve through the ear canal. The type of stimulation (including shape, frequency, pulse width, amplitude, total charge, and energy delivered to the subject) is comparable to the levels applied by commercially available transcutaneous electrical nerve stimulation (TENS) stimulators. The Nesos MAUI PROTECT System is a type of TENS, classified as non-significant risk by the FDA and does not require an IDE.

Although highly unlikely, for participants with any severe or persistently worsening symptoms or adverse reactions, the taVNS therapy will be immediately discontinued, they will be removed from the study, considered treatment failures, and receive medical treatment as necessary. Participants will be taught safe practice with the use of a taVNS unit, such as checking and cleaning skin before starting a session, monitoring skin for signs of irritation, securing electrodes with even pressure distribution and full contact, and watching for signs of unit malfunction requiring maintenance.

Protocol Number: 21-0640

February 1, 2022

The patient manual also provides details for participants regarding the following risks and they are asked to contact their provider and site coordinator if any occur:

The Nesos System exhibits a safety profile similar to that of commercially available TENS units. Possible, but rare, side effects may include:

- Bradycardia
- Skin erosion at electrode site
- Pressure sores
- Unbearable pain at the electrode site
- Undesirable sensation at electrode site
- Uncomfortable stimulation of tissue around the electrodes
- Uncomfortable heating effects, discomfort or burn
- Intermittent stimulation

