4.4 END OF STUDY DEFINITION

Protocol Number: 21-0640

February 1, 2022

A participant is considered to have completed the study if he or she has completed all study tests and visits. If a study participant fails to complete all study tests and does not return for all visits, he or she will be considered lost to follow up. If a participant has an adverse event they will discontinued from the study. Anyone can choose to end their participation at any time.

The study is considered complete once the last participant completes their final study visit, and all identifiable data has been collected and analyzed.

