7.3 LOST TO FOLLOW-UP

A participant will be considered lost to follow-up if he or she fails to complete all study visits and cannot be contacted for the visits. In this event, their participation will be considered complete, and the collected information will be used.

The following actions must be taken if a participant fails to return for a study visit:

- The site will attempt to contact the participant and reschedule the missed visit.
- The site will counsel the participant on the importance of following the study visit schedule and ascertain if the participant wishes to continue in the study.
- Before a participant is deemed lost to follow-up, the investigator or designee will make every effort to regain contact with the participant. This includes up to 3 telephone calls.
- All reasonable efforts will be made to recover equipment, including sending a prepaid label for return.

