8.3 ADVERSE EVENTS AND SERIOUS ADVERSE EVENTS

8.3.1 DEFINITION OF ADVERSE EVENTS (AE)

An adverse event is any untoward medical occurrence regardless of causality assessment. An adverse event can be an unfavorable and unintended sign, symptom, syndrome, or disease associated with or occurring during an investigation, whether or not considered related to the investigation.

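### Section 4.4 takes anyone with an adverse event out of the study and 7.2 bars further data, so willing participants can become retention failures with no 8-week CAPS or PCL-5

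*Protocol*

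**What the plan says.** Four protocol sections govern what happens when a participant has a problem.

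- Section 7.1 separates the device from the study: "Discontinuation of taVNS does not necessarily mean discontinuation from the study, as remaining study procedures may be completed".
- Section 4.4 does not: "If a participant has an adverse event they will discontinued from the study". The definition in 8.3.1 is broad: "An adverse event is any untoward medical occurrence regardless of causality assessment". Section 8.3.4 adds that deterioration of a pre-existing condition is recorded as an adverse event.
- Section 2.3.1, in its part on taVNS risks, covers severe or "persistently worsening symptoms or adverse reactions, the taVNS therapy will be immediately discontinued, they will be removed from the study". It classes these participants as treatment failures and calls the situation highly unlikely.
- Section 7.2 lets a researcher end participation without the participant's consent. For people who withdraw, and equally for those withdrawn by others, it bars further collection: "if s/he is withdrawn from the study, any data already collected will continue to be used, but no new data will be collected". The same section provides safety follow-up: "Participants that prematurely withdraw from the study due to an adverse event will be followed" until the event resolves or the person declines contact.

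Table 1 in Section 6.1.1 makes retention a primary feasibility measure: the percentage completing the baseline and 8-week survey and biological measures, with a goal of 90%. Sections 3 and 8.1 set the feasibility criterion at 70%. Section 9.1 expects 90% and uses the lower confidence limit to plan the future trial. CAPS and PCL-5 at 8 weeks are tertiary outcomes.

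**The concern.** The rules merge two decisions that 7.1 keeps apart: stopping stimulation and leaving the study. Someone who stops the device but would still attend at 8 weeks can be taken out by staff and then not measured.

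Two things are at stake. First, retention would mix unwillingness to return with removal by rule, and its lower limit goes into planning the next trial. Second, the lost 8-week CAPS and PCL-5 scores would plausibly come more often from people doing poorly. Baseline-to-8-week changes and effect sizes would then rest more on those who did well. An analysis plan cannot recover scores that the protocol says not to collect.

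**Working it through.** **1. The passages side by side.** Section 7.1 is permissive: participation need not end, and procedures may be completed as the protocol indicates. A narrower rule elsewhere can therefore stand as an exception, and 2.3.1 can be read that way. The sentence in 4.4 cannot, because it covers every adverse event. It also does not fit 8.3.4, which has investigators ask about events at each visit, track changes in severity and log intermittent episodes among people still on study. Nor does it fit 8.3.3.1, which grades mild events.

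**2. The plan's own figure.** Clopper-Pearson, two-sided 95%, x completers of n = 30: the lower limit is the 2.5% quantile of Beta(x, n−x+1) and the upper limit is the 97.5% quantile of Beta(x+1, n−x). For 90%, x = 27, which gives 0.735 to 0.979, width 0.244, as in Table 2 of Section 9.2. All six rows reproduce, so no stated figure is wrong.

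**3. Effect of one removal.** Retention moves by 1/30 = 3.3 points.

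| Completers | Retention | Lower 95% limit |
|---|---|---|
| 29 | 96.7% | 0.828 |
| 28 | 93.3% | 0.779 |
| 27 | 90.0% | 0.735 |
| 26 | 86.7% | 0.693 |
| 25 | 83.3% | 0.653 |
| 24 | 80.0% | 0.614 |
| 21 | 70.0% | 0.506 |
| 20 | 66.7% | 0.472 |

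Between 24 and 29 completers, each step changes the lower limit by 3.9 points (0.653 − 0.614) to 4.9 points (0.828 − 0.779).

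**4. Where removals sit relative to the expected 90%.** The protocol gives no removal count, so both cases are assumptions.

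- The 90% already covers loss for any reason. Keeping one or two of the three expected non-completers gives 28/30 (lower limit 0.779) or 29/30 (0.828).
- Removals come on top of the 90%. One gives 26/30 (0.693), below the 90% goal; three give 24/30 (0.614).

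**5. The 70% criterion.** 27 − 6 = 21 and 21/30 = 70.0%, which still meets it; 27 − 7 = 20 and 20/30 = 66.7%, which does not. If true retention is 90% and an assumed 10% of would-be completers are removed, p = 0.9 × 0.9 = 0.81 and P(X ≥ 21) = 0.955.

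**6. Tertiary means.** If r of n people are removed and their mean change is d SD worse than the group's, the observed mean shifts by r·d/(n − r). Assumed range: r = 1 to 3 pooled, d = 0.5 to 1.5. Arm sizes of 20 and 10 follow from 2:1 allocation of 30 (Section 6.3).

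| Mean | Shift (SD) | Standard error (SD) |
|---|---|---|
| Pooled, n = 30 | 1×0.5/29 = 0.017 to 3×1.5/27 = 0.167 | 1/√30 = 0.183 |
| taVNS, n = 20, r = 1 | 0.5/19 = 0.026 to 1.5/19 = 0.079 | 1/√20 = 0.224 |
| Sham, n = 10, r = 1 | 0.5/9 = 0.056 to 1.5/9 = 0.167 | 1/√10 = 0.316 |

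Removals in the two arms push the taVNS-sham contrast in opposite directions. Its standard error is √(1/20 + 1/10) = 0.387 SD.

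**The case against.** The other side has a good deal to say.

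- **4.4 is loosely worded and not meant literally.** Sections 8.3.3.1 and 8.3.4 only make sense if people with adverse events stay on study. This is probably right, and it limits how many removals to expect. It leaves the sentence in force as an instruction to staff.
- **2.3.1 does not contradict 7.1.** This stands. A reader might infer that 2.3.1, 4.4 and the pregnancy rule in 8.3.7 all contradict 7.1. Because 7.1 is permissive and defers to the rest of the protocol, only 4.4 clearly does.
- **Worsening PTSD does not by itself mean removal.** Section 2.3.1 separately provides assessment and referral for worsening mental health, and its removal sentence sits among device risks. So selective loss of people doing poorly is plausible, not established.
- **Treatment failures are already a class.** An analysis plan could say how they count. That would not supply their 8-week scores.
- **Adverse-event follow-up in 7.2 is safety follow-up, and the bar is on research data.** That is a natural reading. It also confirms that the 8-week outcome measures are lost.
- **The 90% is most naturally all-cause.** Table 1 counts completed measures whatever the reason for loss. The case that adds removals on top is therefore the less likely one.
- **Removals should be rare and the outcomes are descriptive.** Section 2.3.1 calls its case highly unlikely and reports no serious adverse events or unanticipated device effects in more than 200 users. The tertiary results are for hypothesis generation, with stated caution about effect sizes. This limits the size of the problem.

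**Conclusion.** The point holds as a fault in the withdrawal rules, of minor to moderate size. The sentence in 4.4 conflicts with 7.1 and 8.3.4. Together with 2.3.1 and the bar in 7.2, it can turn willing participants into retention failures with no 8-week CAPS or PCL-5.

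The size depends on a removal count that the protocol does not give and that is probably small. Each removal costs 3.3 points of retention and about 4 to 5 points of its lower limit. If the future trial keeps the same rules, the lower retention figure is the right planning input; the cost is then the data lost from willing people.

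A reader might infer that the feasibility conclusion is at risk or that the treatment contrast is biased in a known direction. The documents do not support either. Seven removals on top of 27/30 are needed to miss 70%. Under the assumed inputs, the shifts in means are smaller than their standard errors, and the direction of any effect on the contrast is unknown.

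The pregnancy rule and the lost-to-follow-up label are side issues. Section 4.4 applies that label to anyone who "fails to complete all study tests and does not return for all visits, he or she will be considered lost to follow up", while 7.3 requires that the person "fails to complete all study visits and cannot be contacted for the visits". Retention counts completed measures, so the label changes no result.

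**What to change.** - In 4.4 and 2.3.1, replace removal from the study with stopping the device where clinically indicated.
- In 7.2, limit the bar on new data to participants who withdraw consent or for whom further assessment is unsafe, and exempt adverse-event follow-up from it. Invite all others to the scheduled 8-week survey, CAPS and biological measures, as 7.1 already allows.
- Report staff-initiated withdrawals separately from participant drop-out. Reasons for withdrawal are already recorded.
- Optional tidying: in 8.3.7, stop the device but keep the survey and CAPS, and omit or flag biological measures that pregnancy affects; align the lost-to-follow-up wording in 4.4 with 7.3.

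The cost is wording in three sections (four with 8.3.7) and any matching consent text. The visit is already scheduled, and clinicians keep every safety decision. The downside is that some 8-week data will come from people who stopped the device, which can be recorded and described. Section 4.1 means the pilot to replicate the larger trial's methodology, so correcting the rules now also keeps them out of that trial.

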7.3 LOST TO FOLLOW-UP

A participant will be considered lost to follow-up if he or she fails to complete all study visits and cannot be contacted for the visits. In this event, their participation will be considered complete, and the collected information will be used.

The following actions must be taken if a participant fails to return for a study visit:

- The site will attempt to contact the participant and reschedule the missed visit.
- The site will counsel the participant on the importance of following the study visit schedule and ascertain if the participant wishes to continue in the study.
- Before a participant is deemed lost to follow-up, the investigator or designee will make every effort to regain contact with the participant. This includes up to 3 telephone calls.
- All reasonable efforts will be made to recover equipment, including sending a prepaid label for return.

8 STUDY ASSESSMENTS AND PROCEDURES

8.1 EFFICACY ASSESSMENTS

Aim 2: Primary Outcome Measure: Feasibility will be evaluated using criteria suggested by Leon⁹⁹: 1) rates of recruitment (per month), 2) adherence to the taVNS intervention, 3) 8-week retention, and 4) duration and completion rate of study assessments. Feasibility is defined as the ability to recruit 75% of eligible, approached, participants and to demonstrate intervention adherence and retention rates of 70% each (Table 1). **Secondary Outcome Measure:**

Protocol Number: 21-0640

February 1, 2022

Acceptability will be evaluated by assessing: 1) time to completion of questionnaires, 2) percentage of missing data from questionnaires, 3) time to completion of the biological data and blood draw, 4) rate of refusal of biologic measurements and blood draw, and 5) score on the taVNS Satisfaction and Usefulness Questionnaire¹⁰⁰ (Table 1). **Tertiary Outcome Measures** include potential taVNS endpoint measures. At the baseline and 8 week follow-up visits, validated self-report MH measures, including assessments of PTSD,⁹⁴ anxiety,¹⁰¹ depression,¹⁰² sleep,¹⁰³ and the CAPS interview⁹⁵ (at screener and follow-up) will be administered. To examine **potential mechanisms of action** and any acute and longer-term change in these mechanisms, the biological measures will be administered at baseline 10 minutes before using the device, again one time at the 8-week follow-up visit. Blood will be drawn to assess markers of inflammation before using the device, after using the device, and again at the 8 week follow-up visit. This allows us to collect data to understand potential acute and long-term effects. These tertiary outcome measures and potential mechanisms of action will be used to inform the

design of a future, RCT to evaluate taVNS efficacy. Measurement quality, amount of missingness or non-response, length of measurement collection, and costs will be assessed. These measures will also be used to provide parameter estimates for power calculations for a future RCT (Table 1). We will also use the preliminary efficacy results from this pilot to generate hypotheses regarding potential mechanisms of action including the various inflammatory, neural and cardiovascular changes that correlate with treatment outcomes

Demographics and MH Treatment Variables: Demographics including age, gender, race, ethnicity, and education will be collected using self-report questionnaires, which will be designed in REDCap and recorded using i-Pads. *Past and current MH treatment data will be collected, including psychotherapy sessions, duration of treatment, and medications used, to be explored as potential covariates in a larger RCT.* Information on perceived barriers to engagement in MH care will also be gathered. Differences between baseline and post-treatment mental health measures will be used to generate hypotheses for a future larger RCT targeting PTSD symptoms as a primary outcome, and anxiety, depression, and sleep quality as secondary outcomes, in order to evaluate taVNS efficacy among a larger sample of WTC responders with PTSD.

Planned Data Analysis: The purpose of the pilot study is to determine whether an RCT evaluating the efficacy of taVNS on MH outcomes is feasible, acceptable, and satisfactory for WTC responders with PTSD. Primary outcomes are based on feasibility. Specifically, recruitment, retention, and adherence will be measured as described above. Secondary outcomes are indicators of acceptability including rates of non-response, time to completion of measures, and intervention satisfaction. Tertiary outcomes include MH and biologic measures. All

measures will be described using frequency and percent or mean (SD) as appropriate, overall and by taVNS and sham group, with corresponding 95% confidence intervals to interpret the precision of the estimates. Median and interquartile range may also be used if discrete data are skewed. For the tertiary outcomes measuring MH and biologic data, descriptive statistics for each time point, as well as differences over time, will be calculated. Differences in outcomes will be assessed from the first time point at baseline and the last time point at 8 weeks, for long-term effects. Within-subject correlation of acute and long-term measures will be reported. **Precision of Estimates:** Primary outcome

Table 2.

Precision of estimated proportions given a sample size of 30			
Estimated Proportion	Lower CL	Upper CL	Width
0.70	0.51	0.85	0.35
0.75	0.56	0.89	0.33
0.80	0.61	0.92	0.31
0.85	0.67	0.95	0.28
0.90	0.74	0.98	0.24
0.95	0.80	1.00	0.19

CL=confidence level

Table 2.

Precision of estimated proportions given a sample size of 30			
Estimated Proportion	Lower CL	Upper CL	Width
0.70	0.51	0.85	0.35
0.75	0.56	0.89	0.33
0.80	0.61	0.92	0.31
0.85	0.67	0.95	0.28
0.90	0.74	0.98	0.24
0.95	0.80	1.00	0.19

CL=confidence level

Protocol Number: 21-0640

February 1, 2022

measures are expected to be 75% for recruitment, 90% for retention, and 80% for adherence.

Two-sided 95% confidence intervals for one proportion were calculated using the Clopper-Pearson method, with scenarios varying the expected percent (0.70-0.95), in order to estimate precision given a sample size of 30. The lower confidence level will be used to inform recruitment, retention, and adherence planning in the future RCT (Table 2). **Hypothesis**

Generation: Differences between baseline and post-treatment secondary outcome measures will be used to generate hypotheses for a larger RCT targeting PTSD symptoms (with a particular focus on hyperarousal) as a primary outcome, and anxiety, depression, and sleep as secondary outcomes, in order to evaluate taVNS efficacy. Estimates and variances at each time point will be used to calculate effect sizes to plan the larger RCT. We will be cautious about using our findings from this pilot study to inform underlying assumptions regarding the true magnitude of the effect of taVNS. This is because effect sizes observed in pilot studies are crude, due to the small sample size, and may not be indicative of the true difference in the larger population. We will also use results to generate hypotheses regarding potential mechanisms of action including the various inflammatory, neural, and cardiovascular changes that correlate with treatment outcomes. We will explore whether the impact of taVNS on PTSD symptoms is mediated by biologic measures of physiological reactivity and inflammatory markers (Table 1).

D. Potential Limitations: Ideally, the activity of deep brain structures related to relevant neural circuits would also be measured using fMRI, given their role in mediating stress and the impact that innervation of the vagus nerve has on specific brain areas, such as the Nucleus Tractus Solitarius. Given the scope of this pilot feasibility study, however, it is not possible to conduct fMRIs on 30 participants. This is something that will warrant further exploration in the next phase of study- an RCT with a large sample size powered to detect differences in outcomes and mediational relationships. In addition, the inclusion of participants staying in their current MH treatment may dilute the ability to test the effects of taVNS. However, given that this is a pilot feasibility study and effect sizes will only be used for hypothesis generation, treatment dilution is less of a concern. We are now, however, examining the role of current treatment in an exploratory manner as its potential role as a likely covariate in future RCT analyses (or as a variable on which to block randomize). Finally, should distancing requirements of COVID-19 continue to be a concern in the beginning of the study period, the study team can easily pivot to implementing the focus group and screening procedures over secure video conference, and the survey measures can be completed electronically via a secure email link. Fitting for the taVNS devices as well as biologic measurements can be conducted quickly and safely with all appropriate precautions taken regarding PPE provision and use for both the study staff and the participant.

E. Dissemination: The results of this pilot feasibility study will provide the necessary foundation to inform a larger trial that tests the efficacy of taVNS at multiple WTCHP sites. As such, it is important that the WTCHP providers and the responder community at large are engaged as stakeholders and collaborators to facilitate community dissemination activities. [name] will be integral in these efforts given her strong ties to the WTC provider and responder communities. Updates on study progress and findings will be presented to stakeholders in the WTCHP including at the Biannual WTC Research Grantees meetings and at WTCHP committee meetings (e.g., WTCHP Mental Health Forum, WTC Steering Committee), as well as to patient stakeholder organizations (e.g., 9/11 Health Watch, FealGood Foundation). Additionally, results will be reported to the MH working group for the WTCHP, in which [name] already participates, and at monthly meetings of the Queens WTCHP. Results will also be disseminated in peer-review publications, and will be presented at national and local conferences. This pilot feasibility study is a first, integral step toward bringing the latest advances in non-invasive, easy

Protocol Number: 21-0640

February 1, 2022

to use bioelectronic medicine technology to a population with high rates of PTSD who experience barriers to PTSD treatment engagement and adherence.

